7.2.3. Exploratory Analyses

7.2.3.1. Incidence of Progression to Renal Failure Requiring Dialysis at Day 29

The incidence of progression to renal failure requiring dialysis at Day 29 will be compared between the treatment groups using a MH test of the difference in 2 proportions stratified by intubated or not intubated on Day 1 for patients not on dialysis at Day 1. The estimated MH risk difference will be summarized along with the 95% CI using Mantel-Haenszel stratum weights and the Sato variance estimator. Deaths will be assumed as failures and missing data will be handled as described for the primary analysis of the primary endpoint.

Time to progression to renal failure will also be analyzed using the KM method and compared using a log-rank test stratified by intubated or not intubated on Day 1 as a sensitivity analysis. Hazard ratio and risk reduction will be summarized from a Cox proportional hazards model stratified by intubated or not intubated on Day 1. Confidence intervals (95%) will be presented for the survival estimate at Day 29 based on the complementary log-log transformation. Kaplan-Meier curves for both treatment groups will be produced.

7.2.3.2. Time to Clinical Improvement over 29 Days

In addition, the time to clinical improvement will be evaluated, as defined by live discharge from the hospital, a decrease of 2 points from baseline on a 6-point ordinal scale, or both. Time to clinical improvement will be analyzed using the KM method and compared using a log-rank test stratified by intubated or not intubated on Day 1 as a sensitivity analysis. Hazard ratio and risk reduction will be summarized from a Cox proportional hazards model stratified by intubated or not intubated on Day 1. Confidence intervals (95%) will be presented for the clinical improvement estimate at Day 29 based on the complementary log-log transformation. Kaplan-Meier curves for both treatment groups will be produced.

7.2.3.3. SF-12 PCS and MCS Scores at Day 29 (or discharge), Day 60 and Day 90

SF-12 PCS and MCS scores at Day 29 (or discharge), Day 60 and Day 90 will be compared between treatment groups using an analysis of covariance (ANCOVA), adjusting for age and the randomization stratification factor.

7.2.3.4. EQ-5D-5L Scores at Day 29 (or discharge), Day 60 and Day 90

EQ-5D-5L index and VAS scores at Day 29 (or discharge), Day 60 and Day 90 will be compared between treatment groups using an analysis of covariance (ANCOVA), adjusting for age and the randomization stratification factor.

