#### **9.4.6. Analyses of Exploratory Endpoints**

Incidence of and time to progression to renal failure requiring dialysis at Day 29 will be analyzed in a similar manner as the primary endpoint.

Time to clinical improvement will be analyzed using the KM method and compared using a log-rank test stratified by intubated or not intubated on Day 1.

The SF-12 PCS and MCS scores and EQ-5D-5L index and VAS scores will be analyzed using an ANCOVA, adjusting for age and the randomization stratification factor.

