5.1.3.2. Clinical Improvement

Time to clinical improvement will be evaluated during this study and is defined as a live discharge, a decrease from of least 2 points (ie, #5 to #3) from baseline, or both. A modified 6-category ordinal scale (itemized below) will be used to evaluate clinical improvement.

1. Discharged
2. Hospitalized, not requiring supplemental oxygen
3. Hospitalized, requiring supplemental oxygen
4. Hospitalized, requiring noninvasive mechanical ventilation
5. Hospitalized, requiring invasive mechanical ventilation
6. Death

5.1.3.3. 12-item Short Form PCS and MCS Scores

The Short-Form (SF)-12, version 2 (1-week recall period) is a validated health-related quality of life (HR-QOL) instrument that is widely used across a broad spectrum of disease indications. The SF-12 survey contains 12 questions and covers 8 domains. There is a further stratification into 2 summary measures (Physical Component Summary [PCS] and Mental Component Summary [MCS]) as specified below. The summary measures are scored using a norm-based method (ie, mean = 50, SD = 10), where a score of 50 indicates an average score with respect to a healthy population. Higher scores indicate better quality of life.

- PCS: general health (1 item), physical functioning (2 items), role physical (2 items) and body pain (1 item)
- MCS: vitality (1 item), social functioning (1 item), role emotional (2 items) and mental health (2 items)

The survey is anticipated to be completed in several minutes and can be completed by the patient or via an interviewer (in-person or over the telephone).

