9.3. Sample Size, Power, and Randomization

A sample size of 243 patients (162 ravulizumab + BSC, 81 BSC alone) is required to ensure at least 90% power and detect an improvement in survival from 60% in the BSC alone group to 80% in the ravulizumab + BSC group at Day 29.

This sample size calculation was performed in EAST 6.5 and assumes:

- 1-sided Z-test of the difference in 2 proportions,
- Type I error = 0.025,
- Pooled variance,
- 2:1 randomization on the 2 treatment groups,
- One interim analysis at 50% information which will be after collecting primary efficacy data on approximately 122 patients. The early stopping boundaries for efficacy and futility (non-binding) will be constructed using α -spending function as Lan-DeMets spending function with O'Brien-Fleming flavor and β -spending function as Gamma(-4) ([Lan, 1983](#); [Hwang, 1990](#)).

Considering a nonevaluable rate of 10%, this study is planned to randomize approximately 270 patients (180 ravulizumab + BSC, 90 BSC alone).

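### Time to clinical improvement: no rule for patients who die without improving, and censoring them at death would overstate the Day 29 Kaplan-Meier estimate

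*SAP*

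**What the plan says.** SAP 5.1.3.2 has improvement "defined as a live discharge, a decrease from of least 2 points (ie, #5 to #3) from baseline, or both", on a six-category scale whose worst category is death. A death is therefore never an event.

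SAP 7.2.3.2 reads: "Time to clinical improvement will be analyzed using the KM method and compared using a log-rank test", with stratification by intubation, and protocol 9.4.6 prescribes the same. The SAP adds a stratified Cox model and states: "Confidence intervals (95%) will be presented for the clinical improvement estimate at Day 29". Neither section gives a censoring time, a composite rule or a competing-risk method for patients who die unimproved.

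The SAP's only censoring rules are in 9.5.1 and are written for survival. The Day 29 rule censors at the smaller of 29 days and time on study, and time on study ends at the disposition date for anyone who leaves early. SAP 9.4.5.1 uses the disposition date as the date of death.

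Elsewhere the SAP does set a rule for death:
- SAP 4.1 and 9.4.5: the ventilation, ICU and hospital day counts become days alive and free of each.
- SAP 7.2.2.3 and 7.2.2.4: SOFA and SpO2/FiO2 take the worst value after death.
- SAP 7.2.3.1, renal-failure incidence: "Deaths will be assumed as failures".

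**The concern.** Censoring at death treats a patient who has died as someone who could still have improved, at the rate of those still alive. One minus the Kaplan-Meier curve then estimates improvement in a hypothetical setting without deaths, not the proportion of randomised patients who improve by Day 29. The sample size section plans for heavy mortality that differs between arms, so the distortion would be neither small nor equal across arms. Because the text is silent, two programmers could also produce materially different results from the same plan.

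**Working it through.** **Source of the death rates.** SAP 9.3 plans for an "improvement in survival from 60% in the BSC alone group to 80% in the ravulizumab + BSC group at Day 29", so Day 29 mortality is 40% and 20%. It also says: "A sample size of 243 patients (162 ravulizumab + BSC, 81 BSC alone) is required to ensure at least 90% power". As a check on those inputs, take a fixed-sample one-sided pooled Z-test at 0.025:
- Pooled survival = (0.60×81 + 0.80×162)/243 = 0.7333.
- Null SE = √[0.7333×0.2667×(1/81 + 1/162)] = 0.0602.
- Alternative SE = √[0.24/81 + 0.16/162] = 0.0629.
- Power = Φ[(0.20 − 1.96×0.0602)/0.0629] = Φ(1.305) = 90.4%.

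The planning figures reproduce. The documents give no figure for clinical improvement, so every improvement rate below is an assumption.

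**Model.** Let I be the true proportion improved by Day 29 and D the proportion dead without improving, with constant cause-specific hazards. The cumulative hazard of improvement to Day 29 is H = −ln(1 − I − D) × I/(I + D). Kaplan-Meier with deaths censored at death converges to 1 − exp(−H), which equals 1 − (1 − I − D)^(I/(I+D)). The length of follow-up cancels.

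Two examples:
- BSC, D = 0.40, I = 0.45: 1 − 0.15^(0.45/0.85) = 0.634.
- Ravulizumab, D = 0.20, I = 0.60: 1 − 0.20^(0.60/0.80) = 0.701.

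**Results with deaths of 40% and 20%, all before improvement**

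| True improvement, BSC / ravulizumab | KM, BSC (excess, points) | KM, ravulizumab (excess, points) | True difference | KM difference |
|---|---|---|---|---|
| 30% / 30% | 40.3% (+10.3) | 34.0% (+4.0) | 0 | −6.3 |
| 40% / 40% | 55.3% (+15.3) | 45.7% (+5.7) | 0 | −9.6 |
| 50% / 50% | 72.2% (+22.2) | 57.7% (+7.7) | 0 | −14.5 |
| 45% / 60% | 63.4% (+18.4) | 70.1% (+10.1) | 15 | 6.7 |
| 50% / 70% | 72.2% (+22.2) | 83.3% (+13.3) | 20 | 11.1 |
| 30% / 70% | 40.3% (+10.3) | 83.3% (+13.3) | 40 | 43.0 |

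**Some deaths after improvement.** If only 30% and 15% die before improving, the excess at 50%/50% falls to 13.4 and 5.4 points. At 45%/60%, the 15-point difference shows as 10.5.

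**Log-rank test.** An unstratified log-rank was simulated with 81 and 162 patients, 4,000 trials per scenario, and deaths of 40% and 20%.
- At 50%/50%, censoring at death gave a significant result against ravulizumab in 53.7% of trials. Holding deaths to Day 29 gave 6.3%.
- At 50%/70%, a significant result in favour occurred in 45.0% and 82.5% of trials respectively.

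At 50%/50% the cause-specific hazard ratio really is 0.860/1.279 = 0.67. The test that censors at death is therefore detecting a true difference in that hazard. It is not detecting a difference in the proportion who improve.

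**The case against.** The strongest reply is that censoring at death is written nowhere. The rules in SAP 9.5.1 are for survival. Death is a category of the scale, so a dead patient's status is known to be not improved on every later day. Holding deaths to Day 29 is thus compatible with the text, and under that reading the bias vanishes. This stands: the documents support an unspecified rule with a risky default, not an instruction to censor at death.

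Three stronger readings are tempting and go too far:
- A reader might infer that the analysis is biased against a drug that saves lives. That holds in the table when improvement rates are similar or moderately different. At 30% against 70% the larger absolute excess is in the ravulizumab arm and the difference is slightly inflated, although the relative excess is still larger on BSC (0.403/0.30 = 1.34 against 0.833/0.70 = 1.19). If the drug raised mortality, the distortion could flatter it.
- A reader might infer that the log-rank and Cox analyses are invalid. With deaths censored at death they still address the cause-specific hazard, a recognised but different target. The biased quantity is the Day 29 percentage when read as a probability of improving.
- A reader might infer that this is the only endpoint without a death rule. SF-12, EQ-5D-5L and the Kaplan-Meier analysis of time to renal failure have no stated rule either.

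The endpoint is also exploratory and outside the closed testing procedure, and SAP 7.2.3.2 calls the log-rank comparison a sensitivity analysis, though it names no main one. That limits the consequence but does not remove the gap.

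**Conclusion.** The point holds in conditional form. No rule covers deaths without improvement, and both the ordinary default and the SAP's own survival rule, if carried over, lead to censoring at death. In that case the Day 29 estimate is too high in both arms, by the amounts tabulated. Those sizes rest on constant hazards, assumed improvement rates and the planned mortality. Treating every planned death as preceding improvement makes them upper-end figures for each assumed pair of rates. Severity is low: the primary analysis, its type I error and the ranked secondary endpoints do not depend on this endpoint.

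**What to change.** Add to SAP 7.2.3.2 that a patient who dies without prior improvement is kept in the risk set as not improved and censored at Day 29 in the Kaplan-Meier, log-rank and Cox analyses, with a matching derivation line in SAP 9.5.1. Alternatively, report the Day 29 estimate as a cumulative incidence with death as a competing event; with no other loss before Day 29 the two give the same estimate. Either one recovers the assumed true percentages in the table and matches the composite handling of death used elsewhere in the SAP. SAP 4.1 says the SAP overrides the protocol, so the protocol need not change.

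The cost is one sentence and one line of code, with no new data. The downside is that the hazard ratio then reflects both improvement and death and is no longer cause-specific; the version censored at death can be kept as a labelled sensitivity analysis. The rule should be fixed before results by arm are seen.

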7.2.4. Other Efficacy Analyses

7.2.4.1. Pharmacokinetic and Pharmacodynamic Analyses

Blood samples will be collected to evaluate ravulizumab concentrations over time. Descriptive statistics of ravulizumab concentration data will be presented for patients randomized and treated with ravulizumab for each scheduled sampling time point.

Blood will also be collected to evaluate total and free C5 concentrations. Descriptive statistics will be presented by treatment group and for each scheduled sampling time point. Total and free C5 concentrations will be evaluated by assessing the absolute values and changes and percentage changes from baseline, as appropriate.

By-patient listings of ravulizumab concentrations, as well as total and free C5 concentrations will be produced.

7.2.4.2. Biomarker Analyses

Serum and plasma biomarkers actual values and changes from baseline will be summarized by treatment group over time, as appropriate. By-patient listings of all biomarker data will be produced. Biomarker data will only be summarized at the final analysis at the end of the study.

7.3. Safety Analyses

All safety analyses will be conducted on the SS. All safety data will be presented in by-patient listings. No formal hypothesis testing is planned. Baseline is defined as the last available assessment on or before Day 1.

7.3.1. Study Duration, Treatment Duration, and Exposure

Study duration will be summarized by treatment group for the ITT population and SS. Treatment duration and exposure will be summarized for the ravulizumab + BSC group for the SS. Each patient's study duration, treatment duration, and exposure will be summarized in patient listings, as appropriate.

Study duration will be calculated as the time in days from Day 1 until the date of discontinuation/completion of the study (ie, study duration (days) = the earlier of [data cutoff date or disposition/death date] – Day 1 date + 1). See [Appendix 9.5.1](#) for the definition of the data cutoff date. Treatment duration will be calculated only for those patients randomized and

treated with ravulizumab as the time in days from the first dose date of ravulizumab until the last dose date of ravulizumab (ie, treatment duration (days) = Last Dose Date – First Dose Date + 1).

7.3.2. Adverse Events (AEs)

The AEs will be coded by primary System Organ Class (SOC) and Preferred Term (PT) using MedDRA (version 23.0 or higher).

For the purposes of this SAP, only Treatment-Emergent Adverse Events (TEAEs) will be summarized. TEAEs are AEs that onset on or after Day 1 in the study. Both tabular outputs and listings will be created for TEAEs as described in this SAP; additional details regarding AEs are outlined in [Appendix 9.4.7](#).

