### 1.3. Schedule of Activities

**Table 1: Schedule of Activities**

Period	Screening Period	Primary Evaluation Period							Follow-up Period 	
		D1 	D5 	D10 	D15 	D22	D29/ Discharge 	Early Termination 	D60	D90
Study Day (D)	D -3 to D -1									
Study Window (days)	NA	NA	±1	±1	±1	±1	±1		±7	
Eligibility										
Informed consent	X									
Inclusion/exclusion	X									
Medical history 	X									
Demographics	X									
Study Administrative										
Confirmation of vaccination or appropriate antibiotic prophylaxis against N. meningitidis 	X								X	
Screening Laboratory Tests										
Confirmed positive SARS-CoV-2 test	X									
Chest CT or X-ray 	X									
Pregnancy test 	X						X	X		
Randomization										
Randomized to study drug + BSC or BSC alone		X								
Administration of Study Drug										
Ravulizumab 		X	X	X	X					
Efficacy Assessments										
Survival status										X
Mechanical ventilation status	X									
Hospitalization status										
Intensive care unit status										
Dialysis status										
FiO 2 , SpO 2 , PaO 2 										
Sequential Organ Failure Assessment score	X	X	X	X	X	X	X	X	X	
Safety Assessments										
Electrocardiogram	X						X	X		
Complete physical examination 	X						X	X		
Abbreviated physical examination 		X	X	X	X	X				
Glasgow Coma Scale	X	X	X	X	X	X	X	X		

Period	Screening Period	Primary Evaluation Period							Follow-up Period 	
		D1 	D5 	D10 	D15 	D22	D29/ Discharge 	Early Termination 	D60	D90
Study Day (D)	D -3 to D -1									
Study Window (days)	NA	NA	±1	±1	±1	±1	±1			±7
Body weight	X	X	X	X	X					
Vital sign measurements (predose) 	X	X	X	X	X	X	X	X		
Adverse event review and evaluation	X	<<monitor continuously>>								X
Review safety card 		X 					X 	X 		X 
Safety Laboratory Tests (Predose)										
Clinical chemistry	X	X	X	X	X	X	X	X		
Hematology	X	X	X	X	X	X	X	X		
Coagulation panel and D-dimer	X	X	X	X	X	X	X	X		
Urinalysis	X	X	X	X	X	X	X	X		
Direct Coombs test	X									

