PK/PD/Immunogenicity Tests										
PK 		X	X	X	X	X	X	X		
Total and free C5 		X	X	X	X	X	X	X		
Immunogenicity (predose) 		X					X	X		
Biomarker Tests										
Serum and plasma biomarkers (predose) 	X	X	X	X	X	X	X	X		
Other										
Concomitant medication 	X	<<monitor continuously>>								X
Nonpharmacologic treatments and therapies 	X	<<monitor continuously>>								X
Patient-reported Outcomes										
SF-12							X			X
EQ-5D-5L							X			X

. The Day 1 visit may occur on the same day as Screening.

. Patients randomized to ravulizumab + BSC will receive a weight-based dose of ravulizumab on Day 1 (Table 5). On Day 5 and Day 10, additional doses of 600 mg or 900 mg ravulizumab will be administered (according to weight category) and on Day 15 patients will receive 900 mg of ravulizumab.

. If a patient is discharged before the end of the Primary Evaluation Period (Day 29), the patient will undergo the early discharge assessments. In addition, the patient will be contacted via telephone on Day 29 to assess health status (eg, survival, mechanical ventilation, hospitalization, intensive care unit, and dialysis). Follow-up telephone calls should be performed as planned unless the patient withdraws consent.

. The Early Termination Visit is to be conducted when the patient discontinues from the study during the Primary Evaluation Period. In addition, the patient will be contacted via telephone on Day 29 to assess health status (eg, survival, mechanical ventilation, hospitalization, intensive care unit, and dialysis).

. Additional monitoring will be performed during the 2 follow-up visits to review patient status, including survival and pregnancy, and to obtain information about new or worsening TESAEs. The follow-up will be conducted as a telephone call if the patient is discharged from the hospital or an in-person visit if the patient is still hospitalized.

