#### **8.4.10. Hospital Discharge**

If a patient is discharged before the end of the Primary Evaluation Period, the patient will be contacted via telephone on Day 29 to assess health status (survival, mechanical ventilation, hospitalization, intensive care unit, and dialysis).

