#### **8.4.11. Follow-up Monitoring**

Follow-up visits will be conducted as indicated in the SoA ([Table 1](#)) to review patient status; including survival, monitoring for pregnancy, and to obtain information about new or worsening treatment-emergent SAEs (TESAEs). The follow-up visits will be conducted as a telephone call if the patient is discharged from the hospital or an in person visit if the patient is still hospitalized.

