#### **8.6.1. Time Period and Frequency for Collecting AE and SAE Information**

All AEs and SAEs will be collected from the time of informed consent until through the timepoints specified in the SoA (Table 1).

All SAEs will be recorded and reported to Alexion or the designee immediately and under no circumstance should this exceed 24 hours, as indicated in Section 10.3 (Appendix 3). The Investigator will submit any updated SAE data to Alexion within 24 hours of it being available.

Investigators are not obligated to actively seek AE or SAE data after conclusion of the study participation. However, if the Investigator learns of any SAE, including a death, at any time after a patient has been discharged from the study, and he/she considers the event to be reasonably related to the study intervention or study participation, the Investigator must promptly notify Alexion.

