5.2.1. Adverse Events (AEs)

Adverse events are defined in Protocol Section 10.3.

All AEs and SAEs will be collected from the signing of the informed consent form (ICF) until the last visit at the time points specified in the Schedule of Activities (SoA) (see Protocol Section 1.3).

For the purposes of this SAP, 4 types of AEs will be noted:

- Pre-treatment adverse events and serious adverse events (PTAEs and PTSAEs)
- Treatment-emergent adverse events (TEAEs)
- Treatment-emergent serious adverse events (TESAEs)

The PTAEs/PTSAs are the AEs/SAEs that occur between the signing of informed consent and Day 1. The TEAEs/TESAEs are AEs/SAEs with onset on or after Day 1.

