9.4.7. Adverse Events

The analysis of AEs is described in [Section 7.3.2](#).

Treatment-emergent AEs are events with onset dates on or after Day 1 in the study. If the start date of an AE is partially or completely missing and the end (stop) date and time of the AE does not indicate that it occurred prior to Day 1, then the determination of treatment-emergent status will be based on the following:

- If the start year is after the year of Day 1, then the AE is treatment-emergent; else,
- If the start year is the same as the year of Day 1 and
 - the start month is missing, then the AE is treatment emergent; else if

- the start month is present and is the same or after the month of Day 1, then the AE is treatment-emergent; else,
- If the start date is completely missing, then the AE is treatment-emergent.

All other AEs are considered PTAEs.

Patient percentages will be based on the total number of patients in the particular treatment group.

AEs with missing relationship will be assumed to be related to study treatment. AEs with missing toxicity grade will be summarized as a separate category.

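### The documents conflict on whether non-serious adverse events are collected after Day 29, and the SAP's TEAE tables have no end date or period split, so they can pool time with different ascertainment

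*SAP*

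**What the plan says.** **Definition.** SAP 7.3.2 states: "TEAEs are AEs that onset on or after Day 1 in the study". SAP 9.4.7 repeats it: "Treatment-emergent AEs are events with onset dates on or after Day 1 in the study". Neither gives an end date.

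**Tables.** SAP 7.3.2.1 to 7.3.2.4 summarise all TEAEs, TESAEs, non-serious TEAEs and toxicity Grades 1 to 5. In SAP 7.3.2.2 the percentage denominator is every Safety Set patient in the arm. No table is split at Day 29 or at discharge, and none adjusts for time at risk.

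**Collection after Day 29, serious events named.** SoA footnote 5 gives the purpose of the two follow-up contacts as reviewing status, including survival and pregnancy, and "to obtain information about new or worsening TESAEs". Protocol Table 4 (duration of study) and Protocol 8.4.11 say the same in substance.

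**Collection after Day 29, all events named.** The SoA row "Adverse event review and evaluation" is marked in the Follow-up Period with no limit to serious events. Protocol 8.6.1 has all AEs and SAEs collected from consent through the SoA timepoints. SAP 5.2.1 states: "All AEs and SAEs will be collected from the signing of the informed consent form (ICF) until the last visit".

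**Between discharge and Day 29.** For a patient discharged early, Protocol 8.4.10 says "the patient will be contacted via telephone on Day 29 to assess health status", followed by a closed list of survival, ventilation, hospitalization, ICU and dialysis. SoA footnote 3 gives the same five items as examples. The SoA nevertheless shows adverse events as monitored continuously through the Primary Evaluation Period.

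**The concern.** The percentage of patients with a TEAE can be read only if the period over which events were sought is known and is the same for everyone counted. Here it may be neither. A site that works from footnote 5 or 8.4.11 would ask about serious events at Days 60 and 90. A site that works from the SoA row or 8.6.1 would ask about all events. The SAP would put both in one percentage.

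Two further features widen the range of observation. SAP 9.5.1 sets the first data cutoff at the last patient's Day 29 visit, so follow-up at that cut runs from 29 to about 90 days per patient. Within Days 1 to 29, a discharged patient leaves bedside monitoring, and the one later contact listed in that period does not name adverse events.

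The incidence of TEAEs and TESAEs is the protocol's stated safety endpoint and compares the arms. The tables exposed are those for all TEAEs, non-serious TEAEs and toxicity grade.

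**Working it through.** The documents give no figure to reproduce. The check is a comparison of text, then an illustration of size.

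**1. The collection rule, side by side**

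| Source | Day 60/90 content |
|---|---|
| SoA footnote 5; Protocol Table 4; Protocol 8.4.11 | new or worsening TESAEs named; non-serious events not mentioned |
| SoA adverse event row; Protocol 8.6.1; SAP 5.2.1 | all AEs, no limit to serious events |

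The first group never says that collection is limited to serious events, and footnote 5 presents its content as additional monitoring. The second group does not mention any restriction. No passage says which group governs.

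**2. The Day 29 call**

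SoA footnote 18 assigns the row for nonpharmacologic treatments to the Day 29 call for patients discharged early. The adverse event row carries no such footnote. The documents therefore state continuous monitoring to Day 29 but name no means of achieving it after discharge.

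**3. Time that falls after Day 29**

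Inputs: Day 29 survival S of 0.80 (ravulizumab + BSC) and 0.60 (BSC alone), from Protocol 9.2. Assumptions: constant hazard to Day 29, no later deaths, all survivors followed to Day 90.

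- Hazard: h = −ln(S)/29
- Days alive, Days 1 to 29: (1 − S)/h = 26.0 and 22.7
- Days alive, Days 30 to 90: 61 × S = 48.8 and 36.6
- Share after Day 29: 48.8/(26.0 + 48.8) = 65%; 36.6/(22.7 + 36.6) = 62%

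If deaths are instead spread evenly over Days 1 to 29 (mean day 15), days alive to Day 29 are 0.8 × 29 + 0.2 × 15 = 26.2 and 0.6 × 29 + 0.4 × 15 = 23.4. The shares become 48.8/75.0 = 65% and 36.6/60.0 = 61%. The result is not sensitive to this choice.

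**4. How far the rule moves the percentages**

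Assume the same non-serious event hazard λ in both arms (no drug effect) and deaths spread evenly over Days 1 to 29. The expected incidence counted to day T is S × (1 − exp(−λT)) + (1 − S) × the mean of (1 − exp(−λt)) over t = 1 to 29.

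| λ per day | To Day 29, BSC v ravulizumab | To Day 90, all events collected |
|---|---|---|
| 0.01 | 21% v 23% | 41% v 50% |
| 0.02 | 36% v 40% | 60% v 72% |
| 0.03 | 49% v 53% | 70% v 81% |

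The values of λ are assumed; the documents give none. The gap between arms here comes only from longer survival. Before rounding it is about 2 to 5 points under one rule and 9 to 12 under the other. A table built on a mixture of the two rules has no clear meaning.

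**5. Before Day 29**

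A survivor discharged on Day 10, 15 or 20 is under bedside monitoring for 10/29 = 34%, 15/29 = 52% or 20/29 = 69% of the period. These days are hypothetical; the documents give no discharge distribution.

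**The case against.** A reader might infer from footnote 5 and 8.4.11 that follow-up collects serious events only. The documents do not support that. Protocol 8.6.1 and the SoA row say all AEs, and SAP 5.2.1 agrees with them. Rewriting SAP 5.2.1 alone to match 8.4.11 would put the SAP in conflict with 8.6.1. This objection stands: the finding is a contradiction, and mixed ascertainment depends on how sites resolve it.

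A reader might also infer that ravulizumab, if it shortens hospital stay, would show fewer events by construction. That gives one direction only. Longer survival adds time at risk (26.0 against 22.7 days alive in Days 1 to 29 under the plan's assumptions) and pushes the other way.

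On the Day 29 call, footnote 3 gives examples rather than a full list, footnote 18 adds an item outside it, and early-discharged patients also have discharge assessments. Protocol 8.6.2 prefers open-ended questioning to detect events, and 8.6.3 requires follow-up of reported events at later contacts. So it is not established that adverse events go unasked. The closed list in 8.4.10 still leaves them out.

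Finally, TESAEs and non-serious TEAEs are already tabulated separately, study duration is summarised by arm (SAP 7.3.1), no formal safety testing is planned (SAP 7.3), and collection is bounded by the last visit. These points limit the consequence. None tells a reader over what period non-serious events were sought.

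**Conclusion.** The point holds as a contradiction in the collection rule combined with tables that have no end date or period split. If sites follow the passages that name TESAEs, or differ in which passages they follow, the all-TEAE, non-serious and toxicity-grade percentages pool periods with different ascertainment.

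The time affected is large: about 65% and 62% of days alive to Day 90, given the plan's survival assumptions, constant hazard to Day 29 and no later deaths. These figures measure patient time, not missed events, and the arms differ by only about 3 points. The direction of any bias between arms is undetermined. TESAE tables are largely unaffected, and the primary endpoint is not touched. The change is worth making because the safety comparison is a stated objective and the correction is cheap.

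**What to change.** 1. **Protocol.** Reconcile SoA footnote 5, Table 4 and 8.4.11 with the SoA adverse event row, 8.6.1 and SAP 5.2.1. State one rule for non-serious adverse events after Day 29 and use it in all six places.
2. **Day 29 call.** Add adverse events to its content in Protocol 8.4.10 and SoA footnote 3.
3. **SAP 7.3.2.** Present the all-TEAE, non-serious and toxicity-grade tables for onset from Day 1 to Day 29. Add a later-period table only if non-serious events are actively collected then. Present TESAEs separately for Days 1 to 29 and after Day 29.

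The cost is wording, one extra cut of existing tables and one question on a call already planned. If follow-up is defined as serious-only, late non-serious events reported spontaneously would appear only in listings. The Day 29 cut does not by itself remove the gap after early discharge or the difference in survival time; item 2 addresses the first in part, and the second needs to be kept in mind when the tables are read.
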